6.6 Possible Alternative Treatments

Only patients who require and have already consented to non-penetrating glaucoma surgery will be contacted regarding participation in this study. They will undergo the same non-penetrating glaucoma surgery regardless of whether they participate in the study or not. The only differences in their treatment will be any adaptations to the surgery required by the ARGOS-SC implant related procedures, such as placement of the ARGOS-SC implant, access to the suprachoroidal space and a slightly longer surgery time.

Treatment decisions during the follow-up period will be based primarily on IOP measurements obtained using conventional tonometry. Abnormalities in IOP detected through measurements obtained with the ARGOS-SC device may however result in additional clinic visits for further diagnosis. If potential subjects choose not to participate in the study, their IOP levels will be monitored using their physician's preferred method.

6.7 Risk/Benefit Assessment

Based on the risk management effort, and the resulting design implementation and user information, the Implandata management team concludes that the benefits for a patient from the implantation of an ARGOS-SC implant device outweighs the residual risks as described above. Predicate implantable ophthalmic medical devices and procedures, show that there is also residual risk with regard to the surgical procedure in general. The surgical placement method of the ARGOS-SC implant slightly differs from non-penetrating glaucoma surgery, but there is no significant difference in the risk profile for the patient. The medical benefit of the implantation of the device, and resulting possibility of direct IOP measurement and frequent self-tonometry by the patients at home clearly outweighs the identified residual risks of the device. The residual risks and their probability of occurrence are within the acceptable range, compared to similar marketed devices in the ophthalmic field.

Being able to monitor IOP quasi-continuously over extended periods of time will give the treating ophthalmologists valuable information about the individual disease of a patient and the effectiveness of the medication regimen. The ARGOS-SC system will help the patients to actively monitor their condition, which will in turn improve their motivation and ultimately compliance. This is particularly important in a disease where the loss of vision normally occurs gradually over long periods of time and is often only recognized in advanced cases.

7. OBJECTIVES AND HYPOTHESES OF THE CLINICAL INVESTIGATION

7.1 Objectives

The purpose of this study is to evaluate the safety and performance of the ARGOS-SC suprachoroidal pressure sensor in patients with glaucoma undergoing non-penetrating glaucoma surgery.

7.1.1 Primary Objectives

Performance

• To evaluate the limits of agreement between measurements with the Goldmann Applanation tonometry (GAT), Pascal Dynamic Contour Tonometry (DCT) and the ARGOS-SC system in the 12 months following implantation.

7.1.2 Secondary Objectives

Safety

• To evaluate the safety and tolerability of the ARGOS-SC pressure sensor during the implantation and throughout a 12 months follow-up period.

Performance

• To evaluate the performance of the ARGOS-SC system up to 12 months after implantation

7.2 Claims and intended performance of the IMD to be verified

This study is designed to show agreement between IOP measurements obtained with the ARGOS-SC device, GAT and DCT at the same time point. Furthermore, it will allow initial assessment of the safety of implanting the ARGOS-SC sensor during non-penetrating glaucoma surgery.

7.3 Risks and anticipated adverse device effects to be assessed

Information will be collected on all AEs and ADEs to allow assessment of the safety of implantation and use of the ARGOS-SC sensor in humans undergoing non-penetrating glaucoma surgery. Particular attention will be paid to ophthalmic AEs, for which increased risks are considered possible. However, because these AEs are common in this patient population, an independent assessment of their relationship to the ARGOS-SC sensor implant will not be possible. Possible adverse device effects will be subject to evaluations of the DSMB. Incidence, nature and severity will be compared to literature of standalone NPGS. AEs of particular interest include:

• Perforation/Rupture of the trabeculo-descement's membrane (TDM)

- Anterior chamber inflammation
- Hypotony (IOP < 5 mmHg for more than one month or hypotony maculopathy (e.g. with signs of maculopathy))
- Shallow anterior chamber
- Suprachoroidal hemorrhage
- Choroidal detachment
- Retinal detachment
- Hyphema
- Iris incarceration in TDM
- Temporary visual impairment as a secondary effect caused by the adverse events described above

Procedures that are anticipated in the general patient population in the follow-up period include:

- 360°-suture removal after canaloplasty
- Nd:YAG membranectomy
- Nd:YAG goniopuncture
- Nd:YAG iridotomy
- Retinal detachment repair
- Transcleral cyclophotocoagulation
- Vitrectomy with epiretinal membrane peeling
- Choroidal drainage
- Anterior chamber infusion with or without recombinant tissue plasminogen activator
- Re-suturing of the scleral flap
- Subconjunctival injection of dexamethasone
- Inserting a therapeutic soft contact-lens

8. DESIGN OF THE CLINICAL INVESTIGATION

8.1 General Aspects

8.1.1 Description of the type of clinical investigation

This prospective, open-label, single-arm multicenter clinical investigation will enroll only adult patients who are planning to undergo indicated non-penetrating glaucoma surgery for the treatment of glaucoma.

Prospective patients will undergo informed consent and screening up to 28 days prior to the planned surgery. Following surgery, all patients who receive an ARGOS-SC implant will attend additional 8 scheduled follow-up visits during the 12-month post-surgical period (days 1, 3, 10, 30, 90, 180, 270 and 360).

To investigate the performance of the device and detect possible safety issues, patients will undergo ophthalmic examinations and be questioned regarding their health by the investigator at every visit.

Additional visits may be held as deemed appropriate by the investigator. The content and reasons for visits will be documented on a separate unscheduled visit CRF.

8.1.2 Description of the measures to be taken to minimize or avoid bias

No randomization or blinding/masking procedures will be used in this study. To avoid bias resulting from patient selection, all consecutive patients who potentially meet the eligibility requirements will be informed of the study and asked to participate. Those agreeing will undergo the informed consent procedure and if they consent, will be screened. All eligible patients will be enrolled.

There will be no control group for safety events. Incidence, nature and severity will be compared to literature of standalone NPGS. To allow assessment of performance, measurements of IOP with the ARGOS-SC sensor will be compared to those obtained with the standard GAT method and Pascal DCT at the same time point. To prevent possible influence of prior knowledge of the IOP value obtained with the ARGOS-SC, which is objectively displayed, measurements will always be made first with GAT/DCT. Data on all device deficiencies will be recorded.

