Detailed implantation instructions are presented in the Instructions for Use (IFU) [16] and the Investigator's Brochure (IB) [17] and in Section 8.3.14 Surgery of this CIP.

Following completion of the IOP lowering portion of the non-penetrating glaucoma surgery, hyaluronic acid-based viscoelastics such as Healon OVD (Abbott Medical Optics Inc.) are used to separate the sclera from the choroid. The scleral flap is enlarged or an additional small incision made next to it to ensure a final flap width of at least 3.2 mm to 3.5 mm. The ARGOS-SC sensor is then gently pushed through the opening into the suprachoroidal space with the "pressure sensing side" of the ASIC facing the eye.

Page 31 of 97

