8.3.2 Exclusion Criteria

Eligible subjects must not meet any of the following exclusion criteria:

- 1. Contraindications for a non-penetrating glaucoma surgery
 - Neovascular glaucoma, primary and secondary angle closure glaucoma
 - Condition after previous glaucoma surgery
 - ➢ IOP > 40 mmHg
- 2. Myopia (> -6 dpt) or hypermetropia (> +4 dpt)
- 3. Axis length < 22 mm or > 26 mm
- 4. Patient with single eye vision (monovision)
- 5. Exudative age-related macular degeneration, instable macular degeneration 30 days prior to inclusion, or macular edema
- 6. Acute retinal detachment

- 7. Uncontrolled Diabetes Mellitus (DM) with manifestation of moderate to severe nonproliferative diabetic Retinopathy (DR) or proliferative DR.
- 8. History or evidence of severe active inflammatory eye diseases (i.e. uveitis, retinitis, scleritis) in one or both eyes within 6 months prior to ARGOS-SC implantation
- 9. Ocular surgery procedure(s) (excluding selective laser trabeculoplasty and peripheral iridotomy) within 6 months (cataract surgery within 3 months) prior to ARGOS-SC implantation in the study eye that can affect the assessment of IOP by Goldmann Applanation tonometry/Pascal Dynamic Contour Tonometry
- 10. Ocular disease other than glaucoma that may affect assessment of visual acuity and/or IOP by Goldmann Applanation tonometry (e.g. choroidal hemorrhage or detachment, lens subluxation, thyroid ophthalmopathy)
- 11. Existence of other active medical eye implant and/or other active medical implants in the head/neck region
- 12. Difficulties or complications during NPGS procedure or implantation of ARGOS-SC sensor, as assessed by surgeon (e.g. perforation of trabeculo-descement's membrane, excessive aqueous filtration through TDM leading to shallow anterior chamber, excessive bleeding, choroidal detachment).
- 13. Severe generalized disease resulting in a life expectancy shorter than a year
- 14. Currently pregnant or breastfeeding
- 15. Participation in any study involving an investigational drug or device within the past 30 days or ongoing participation in a study with an investigational drug or device
- 16. Patients who are not suitable for the study based on the surgeon's evaluation (e.g. Persons affected by Parkinson's disease or essential tremor)
- 17. Patients unable or unwilling to understand or comply with required study procedures
- 18. Patients with psychiatric disorders influencing their judgement or autonomy

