8.3.3.3 Premature subject withdrawal

Subjects will be informed that they have the right to withdraw from the study at any time. The investigator must determine whether voluntary withdrawal is due to a cause that could raise safety concerns.

All subjects who withdraw from the study after implantation and before completing the follow-up visits per protocol will be considered to be drop-outs. Subjects who drop-out or are withdrawn after implantation will not be replaced. Unless the patient revokes his/her permission to use it, any data collected up to the point of the patient's withdrawal will be included in the analysis. The data of all subjects who undergo implantation of the ARGOS-SC pressure sensor will be included in the efficacy analysis under the Full Analysis Set.

A subject will be withdrawn for any of the following reasons:

• The subject withdraws informed consent.

- It is determined during NPGS surgery that the subject is not feasible for ARGOS-SC pressure sensor implantation. Subjects withdrawn before implantation of the sensor will be replaced.
 For subjects determined to be ineligible during NPGS surgery, additional information will be collected about the procedure up to that point.
- The ARGOS-SC pressure sensor must be removed for any reason.

If the subject permits, all end-of-study assessments indicated in the visit schedule will be performed for implanted early discontinuing subjects.

Any subject who has been discontinued from the study because of an AE related to a study device or procedure will be followed as deemed appropriate by the investigator until resolution or stabilization of the event. This will be documented in the medical chart and in the CRF. Any subject who has been discontinued from the study because of an AE not related to a study device or procedure will be followed as deemed appropriate by the investigator.

The investigator will classify the termination reason of each subject at the end of the study in the termination page of the CRF according to the following:

- AE
- Non-compliance with clinical investigation plan (CIP)
- Lost to follow up
- Voluntary withdrawal not for AE
- Other reason

The choice of keeping the implant or letting the implant be retrieved will be offered to the participating patients.

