9.1.3 Safety Analysis

The incidence and nature of adverse events observed within the safety population will be analyzed by descriptive and explorative statistical methods.

Safety will be described in detail by frequency, seriousness, severity, nature and duration of events. Number of adverse events as well as the number and relative frequency of patients reporting adverse events will be tabulated by system organ class and preferred terms. The same table will be prepared for serious adverse events. In addition, the number and relative frequency of patients reporting adverse events will be tabulated by system organ class and preferred terms in dependence on the worst severity and worst causal relationship. Furthermore, number of adverse device effects as well as the number and frequency of patients reporting adverse device effects will be tabulated by system organ class and preferred terms and not by event description as stated in the protocol.

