9.11 Datasets to be analyzed

9.11.1 Safety set

The safety population comprises all subjects for whom ARGOS-SC pressure sensor implantation was attempted, defined as introduction of the ARGOS-SC pressure sensor into the eye, whether or not the implantation was successful.

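### The literature comparison for safety favours the device, because eyes with disqualifying NPGS complications leave before the sensor goes in and are never counted

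*Protocol*

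**What the plan says.** Protocol 7.3 and 8.1.2 plan the same safety comparison: "There will be no control group for safety events. Incidence, nature and severity will be compared to literature of standalone NPGS". Section 7.3 adds that the ophthalmic events are common in these patients, so their relationship to the implant cannot be assessed independently. It lists events of particular interest, among them perforation of the trabeculo-Descemet membrane (TDM), shallow anterior chamber and choroidal detachment.

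The population that is counted is defined elsewhere:

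- **Timing.** Section 4.7 (and likewise 8.3.14.1) places the sensor "Following completion of the IOP lowering portion of the non-penetrating glaucoma surgery".
- **Exclusion 12** (8.3.2; SAP 2.5): "Difficulties or complications during NPGS procedure or implantation of ARGOS-SC sensor, as assessed by surgeon". Its examples are TDM perforation, shallow chamber from excessive filtration, excessive bleeding and choroidal detachment.
- **Replacement.** Patients withdrawn before implantation are replaced (8.1.5, 8.3.3.3).
- **Safety set** (9.11.1; SAP 3.7): "all subjects for whom ARGOS-SC pressure sensor implantation was attempted, defined as introduction of the ARGOS-SC pressure sensor into the eye".
- **Analysis** (9.1.3): "The incidence and nature of adverse events observed within the safety population will be analyzed by descriptive and explorative statistical methods".

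For patients removed on the table, 8.3.3.3 says "For subjects determined to be ineligible during NPGS surgery, additional information will be" gathered on the operation up to that point. No analysis in the Protocol or SAP uses it. SAP 4.6.2 lists the safety tabulations and contains no literature comparison.

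**The concern.** Three of the four examples in exclusion 12 are also events of particular interest in 7.3. Eyes are therefore removed for the very events whose incidence is then set against published NPGS figures, and nothing in the plan restricts the published figures in the same way.

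The comparison carries weight because 7.3 concedes that attribution to the implant cannot be settled event by event. It appears in 8.1.2 under measures against bias. That section presents consecutive recruitment as the protection against selection and does not mention selection during surgery. If the observed incidence looks similar to or lower than the literature, the natural reading is that the implant adds no risk to NPGS. Part of that result could come from who was left in the denominator.

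**Working it through.** **No plan figure to reproduce.** The documents give no NPGS event rate, no literature source and no expected share of eyes removed under exclusion 12. The only fixed input is 24 patients (8.3.7). All rates below are assumptions, with the device taken as neutral.

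**Step 1: follow one eye through the rules.** A TDM perforation occurs during the dissection, is seen, and is judged disqualifying.

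- Exclusion 12 removes the patient, no sensor is introduced, and a replacement is recruited.
- The patient is not in the safety set, so the event is in neither numerator nor denominator.
- In a published series counting every operated eye, the same eye is in both.

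**Step 2: events before the sensor.** Let c be the share of operated eyes removed for such complications.

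- All-operated rate = c. Contribution to the safety set = 0.
- Operated eyes needed to fill 24 = 24/(1 − c).
- Chance that 24 unselected eyes include at least one such event = 1 − (1 − c)^24.

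| c | All-operated rate | Safety set | Eyes operated to fill 24 | Removed | Chance of ≥1 in 24 unselected eyes |
|---|---|---|---|---|---|
| 5% | 5% | 0% | 25.3 | 1.3 | 71% |
| 10% | 10% | 0% | 26.7 | 2.7 | 92% |
| 20% | 20% | 0% | 30.0 | 6.0 | over 99% |

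Restoring the removed eyes recovers the right rate: 1.3/25.3, 2.7/26.7 and 6.0/30.0 give 5%, 10% and 20%.

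**Step 3: later events.** Let e0 be the later-event rate in uncomplicated eyes and k the relative risk in complicated eyes.

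- All-operated rate = c·k·e0 + (1 − c)·e0. Safety-set rate = e0.
- Ratio of safety set to all-operated = 1/(1 + c(k − 1)).

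| k | c = 5% | c = 10% | c = 20% |
|---|---|---|---|
| 1 | 100% | 100% | 100% |
| 2 | 95% | 91% | 83% |
| 5 | 83% | 71% | 56% |

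With e0 = 5%, k = 5 and c = 10%, for example, the all-operated rate is 0.10 × 25% + 0.90 × 5% = 7%, and 5/7 = 71%. If complicated eyes carry no extra later risk (k = 1), there is no bias.

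**Step 4: start of recording.** Section 8.3.13.4 starts adverse event recording at implantation, while 8.3.17 and 11.3 start it at consent. Under the first rule, even an implanted eye's pre-sensor event would go unrecorded. Under the second it would count.

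**The case against.** The other side has several fair points.

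- **No decision rests on this comparison.** Success under 9.5 needs at most one of 24 patients with a serious adverse device effect (SADE), plus the agreement criterion. The DSMB can stop implantation, and the safety analysis is descriptive. This stands. A reader might infer that the literature is the study's only safety standard. It is only the only external one, and the fixed SADE limit does not depend on it. That limit does not replace the comparison either, because it counts only serious device-related events.
- **The literature is unidentified.** It may be restricted in some way. This stands, and the finding is conditional on it. Leaving the comparator's eligibility open is part of the gap.
- **Removed patients are not invisible.** Section 8.1.5 makes them screen failures, and 9.1.2 and SAP 4.3 tabulate screen failures with reasons. This stands, but no text links that table to the literature comparison.
- **The safety-set rate of TDM perforation is not zero by design.** A reader might infer that it is. Exclusion 12 works on the surgeon's judgement, so an unrecognised or accepted perforation can go on to implantation. Section 6.3 also lists perforation as a possible complication of the combined procedure, and such eyes stay in the set once the sensor has been introduced.
- **Later events need not be biased.** Hypotony, for instance, is defined in 7.3 by a duration of over one month or by maculopathy, so hardly any of it can precede the sensor.

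A reader might also infer that a doubled risk would pass unnoticed. With q the share of literature events falling before the sensor and RR the implant's relative risk, the observed rate is the literature rate times (1 − q)RR, which equals the literature rate at RR = 2 and q = 50%. The documents support no value of q and contain no rule comparing an observed count with a literature count. A probability of false reassurance therefore cannot be derived from the plan.

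**Conclusion.** The point holds in limited form. Timing of placement, exclusion 12, replacement and the safety-set definition together remove eyes whose NPGS complication is recognised and judged disqualifying before the sensor is introduced. If the published rates cover all operated eyes, the comparison in 7.3 and 8.1.2 favours the device. For those pre-sensor complications the direction is certain and the shortfall equals the share of eyes removed. For later events the shortfall runs from none upward: under the assumptions shown, the safety set would display between 100% and 56% of the all-operated rate. The documents do not support the broader reading that all event rates must look lower than the literature, since a real device effect could still push them above it. The SADE criterion in 9.5 is unaffected. The plan should be changed, because the needed denominator comes largely from data already being collected.

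**What to change.** Amend 7.3 and 8.1.2, and add the comparison to the SAP safety analysis (4.6.2), which now lacks it.

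1. **Intraoperative NPGS events.** Compare with the literature over all consented patients in whom NPGS was started, including those removed during surgery under exclusion 12. Use the procedure information from 8.3.3.3 and the screen-failure reasons from 9.1.2 and SAP 4.3. Show removals during surgery separately from earlier screen failures.
2. **Safety-set events.** Compare only those with onset after sensor introduction. Name the literature in advance and use sources with matching eligibility and denominator where they exist. Where only all-operated rates are available, state that the comparison favours the device and draw no conclusion that risk is not increased.
3. **Start of recording.** Reconcile 8.3.13.4 with 8.3.17 and 11.3, since part 1 needs events from the start of NPGS in implanted and removed patients alike.

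The cost is wording in both documents and one more denominator. No patients, procedures or clinical rules change. The drawbacks are that fewer published figures may qualify, and none may match fully, and that the comparison becomes less favourable to the device.

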8.1.3 Primary and secondary endpoints

8.1.3.1 Primary endpoints

Performance

Level of Agreement between measurements made using GAT and the ARGOS-SC system from V02 (day 1) through V04 (day 10) and with GAT, Pascal DCT and the ARGOS-SC system from V05 (day 30) through V09 (day 360).

8.1.3.2 Secondary endpoints

Safety

- Number of patients experiencing a device-related SAE (SADE) at any time during implantation and in the first 12 months (Day 0 to Day 360) following it.
- Incidence, nature, severity and seriousness of observed adverse events and adverse device events at any time during implantation and 12 months following it.

Performance

- Repeatability of the ARGOS-SC measurement
- Incidence, nature and seriousness of observed device malfunctions during implantation and in the 12 months follow-up

Utility

- User acceptance of the ARGOS-SC implantation procedure by means of evaluation of implantation procedure questionnaires (investigators)
- User acceptance of the ARGOS-SC system at the investigational site by means of evaluation of patient acceptance questionnaires (by investigators)
- User acceptance of the ARGOS-SC system at home by means of evaluation of patient acceptance questionnaires (patients)
- Daily IOP self-measurement profiles (patients)

8.1.4 Equipment to be used to assess the clinical investigation variables and arrangements for monitoring maintenance and calibration

Sites will use their own diagnostic devices. The study monitor will verify that the sites maintain and calibrate these devices on a regular basis.

Page 52 of 97

